8. RECRUITMENT METHODS

8.1 Methods

8.1.1 Recruitment

Eligible patients will be pre-screened by PI on a weekly basis, who will then email the primary radiation oncologist. The primary radiation oncologist will determine if the intervention is acceptable to offer to the

potential patient at the time of consultation, and this will inform the provider acceptability ratio, one of the primary outcomes of the study. The primary radiation oncologist will discuss the study with the patient at the time of consultation and, if the patient is interested, will notify the research team to facilitate consent for enrollment.

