9. STUDY PROCEDURES

9.1 Screening Visit

9.1.1 Informed Consent/Accent/HIPAA Authorization (Appendix 4)

The Informed Consent Process will take place at screening.

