12. DATA ANALYTICS

12.1 Study Objectives

Primary:

The primary objective of this study is to evaluate the feasibility of conducting a randomized trial of an exercise coaching program to encourage physical activity for women treated with adjuvant pelvic intensity-modulated radiation therapy treatment for endometrial cancer.

Secondary:

- 1) To collect initial efficacy evaluation of the exercise coaching program on patient-reported fatigue, bowel/urinary toxicity, QoL, cognitive function, sexual function and satisfaction, and self-efficacy, as well as distance walked during 6MWT between the immediate and delayed-start group from baseline to pre-specified time points (end of RT, 5-7 weeks post RT, and 16-19 weeks post RT) to guide statistical planning for follow-up study.
- 2) To measure the prevalence of fatigue at baseline in the population of endometrial cancer patients recommended pelvic radiation therapy using data collected in the screening process.
- 3) To explore potential behavioral mechanisms (mediators) and variables that influence the strength of the intervention effect (moderators).

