 - a. Individual adherence to the physical activity monitor will be defined as wearing the activity tracker for at least 8 hours a day for 70% of the days in the study. Heart rate will be used to determine wear-time. We set an a priori goal of overall 70% participant adherence to the physical activity monitor, to be analyzed per cohort (6 of 8 participants in each arm demonstrating adherence as defined above).
- 5) Adherence to recommendation of 150 minutes per week of moderate physical activity:
 - a. Individual adherence to regular physical activity will be defined as meeting the recommendation of 150 minutes of moderate physical activity per week, based on the Physical Activity Guidelines for Americans developed by the U.S. Department of Health and Human Services (HHS). The target for participant adherence is set at an a priori goal of 70%.

The *resource and management* feasibility will be assessed based on the capacity of the exercise coach and research team to perform the required tasks of the protocol:

- 1) Adherence to the timeline of study procedures and human and data management issues that could potentially arise during a full-scale RCT will be tracked. Adherence to the study timeline for completion of required patient surveys and 6MWT as well as appropriate scheduling (patient attendance not required) of the exercise coaching sessions and follow-ups will be a proxy measurement of research resource and human data management acceptability. We set an a priori goal of 80% adherence.

Secondary Objective Analytical Plan

- 1) Changes in patient-reported fatigue, bowel/urinary toxicity, QoL, cognitive function, sexual function and satisfaction, and self-efficacy, as well as distance walked during 6MWT from baseline to pre-specified time points (end of RT, 5-7 weeks post RT, and 16-19 weeks post RT) within and between each group will be compared using two-sample t-test or Wilcoxon Rank Sum test when appropriate. Repeated measure models/linear mixed effect models may also be used to explore the changes in self-reported questionnaires over time among different treatment groups. Data will be analyzed based on the intention-to-treat principle and used to estimate treatment effect size for future trial design.
- 2) Prevalence of fatigue at baseline in the population of endometrial cancer patients receiving pelvic radiation therapy will be reported using data collected in the screening process.

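### Baseline fatigue prevalence is labelled for the population recommended or receiving pelvic RT, but on the body text it is measured only in approved, consenting trial candidates

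*Protocol*

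**What the plan says.** Secondary objective 2 (section 12.1, and in near-identical words in section 2.1 and the synopsis) reads: "To measure the prevalence of fatigue at baseline in the population of endometrial cancer patients recommended pelvic radiation therapy using data collected"; the source it then names is screening. The matching analysis item in section 12.2 reads: "Prevalence of fatigue at baseline in the population of endometrial cancer patients receiving pelvic radiation therapy will be reported", and goes on to name the screening process as the data source. So the objective concerns patients *recommended* pelvic RT and the analysis concerns patients *receiving* it.

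Section 8.1.1 describes how a patient gets to screening. First, "Eligible patients will be pre-screened by PI on a weekly basis". Next, "The primary radiation oncologist will determine if the intervention is acceptable to offer to the" potential patient. The oncologist then discusses the study and, "if the patient is interested, will notify the research team to facilitate consent for enrollment".

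Section 9.1.1 adds: "The Informed Consent Process will take place at screening". The 0-10 rating is listed under the same visit (section 9.1.3), and Table 1 marks it in the Screening column only. Section 8.1.2.1 defines screen failures as people who consented but were not entered. Section 16.1.1 gives waiver of consent as not applicable. The only waiver mentioned is a partial HIPAA waiver for the PI's pre-screening (section 16.2.1).

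**The concern.** The population named in the objective and the people who supply the data differ. A woman whose oncologist does not think the study suitable for her, or who is not interested, is still a patient recommended pelvic RT, but nothing in the body text provides a rating from her.

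The steps that remove such patients are plausibly related to fatigue. Eligibility requires ECOG 0-1 and excludes women already doing at least 150 minutes of moderate exercise a week. The oncologist judges suitability for an exercise study, and the patient must want to join one. A very tired patient may decline; a tired patient may equally be drawn by the offer of help. The direction cannot be settled from the protocol.

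Section 1.3 says that the prevalence of fatigue in these women is not well documented. A figure from willing, approved candidates that carries a population label could be taken to fill that gap.

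**Working it through.** The protocol gives no expected prevalence, precision or sample size for this objective, so there is no figure to reproduce. The check has three parts.

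**1. Share of patients rated.** Inputs from section 12.2: provider acceptability goal 50%, patient acceptability goal 50%. The patient-acceptability denominator is not spelled out; I take it to be patients whose oncologist agreed.

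- Rated share if both goals are just met: 0.50 × 0.50 = 0.25 of pre-screened patients.
- Section 12.2 gives about 24 + 24 = 48 pelvic RT courses a year, not stated to be endometrial only. If all 48 were pre-screened (an upper-end assumption), 48 × 0.25 = 12 would be rated in a year.

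**2. What the rated patients say about the unrated.** Let r be the share rated and p the prevalence observed among them. With no assumption about the rest, prevalence among pre-screened patients lies between r·p (no unrated patient fatigued) and r·p + (1 − r) (all of them fatigued). The values of p are assumed.

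| r | p | lower | upper |
|---|---|---|---|
| 0.25 | 0.30 | 0.075 | 0.825 |
| 0.25 | 0.50 | 0.125 | 0.875 |
| 0.25 | 0.70 | 0.175 | 0.925 |
| 2/3 | 0.50 | 0.333 | 0.667 |

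The last row is a favourable case: 32 of 48 rated, where 32 = 16 / 0.50 is the number screened to randomise 16 at the 50% screening-appropriateness goal. All rows concern pre-screened patients, whom section 8.1.1 already describes as eligible. They say nothing about patients recommended RT who are not eligible.

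Modest selection is enough to move the figure. Take a true prevalence of 50% (assumed):

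- If 20% of fatigued and 30% of non-fatigued patients are rated: 0.5 × 0.20 / (0.5 × 0.20 + 0.5 × 0.30) = 0.10 / 0.25 = 40%.
- With the two rates exchanged: 0.15 / 0.25 = 60%.

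**3. Sampling error, which is a separate matter.** Exact (Clopper-Pearson) 95% intervals at an observed 50%: 6/12 gives 21-79%, 8/16 gives 25-75%, 16/32 gives 32-68%. These describe uncertainty about the screened group only and do not cover the selection in part 2.

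**The case against.** The strongest reply is that the protocol names its data source each time it states the objective, and that naming a target population and then the sample used is ordinary wording. That is fair as far as it goes. But the phrase identifies where the ratings come from; it does not narrow the population to which the result is attached. Nor does it explain why that population changes between objective and analysis.

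Other parts of the reply stand:

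- Section 2.1 ties this objective to Appendix 2, which is not shown and could describe wider collection. The absence of a waiver of consent points against that, but the restriction to consenting patients remains a reading of the body text.
- The pre-screened, approved and consented counts will exist anyway, because the primary feasibility outcomes need them. The choice of interval could be left to a statistical analysis plan.
- A follow-up trial that recruits in the same way would mainly need prevalence among its own candidates, which this study does yield.

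A reader might also infer more than the documents support. The protocol does not claim a census or a representative sample of all such patients. The objective is not impossible: prevalence among screened candidates can be reported as planned. No section says that this estimate will set the population or the stratification of the follow-up trial; the purpose of guiding statistical planning is attached to objective 1. And the selection rates above are illustrations, so they establish neither the size nor the direction of any bias.

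**Conclusion.** The point holds as a mismatch between label and data. Objective 2 and its analysis item name two different populations, and on the body text the ratings come from neither as a whole, only from eligible, clinician-approved, interested and consenting candidates. The figure may be biased for either named population, in an unknown direction.

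If the two 50% goals are just met and 50% of rated patients are fatigued, the data alone place prevalence among pre-screened patients anywhere from 12.5% to 87.5%. This rests on the assumed observed value, on the reading of the acceptability denominators, and on Appendix 2 not providing for ratings outside consent. A larger rated share narrows the bounds, to 33-67% at two-thirds.

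This is a minor matter: a descriptive secondary item in a 16-patient pilot without a hypothesis. No primary feasibility criterion depends on it.

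**What to change.** Use one wording in the synopsis, section 2.1, section 12.1 and item 2 of the secondary plan in section 12.2. For example: *the proportion with a fatigue score of 4-10 at screening among all patients who consented and were screened, including screen failures*. The 4-10 cut is the one that the synopsis already uses for stratification.

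Report the proportion with an exact 95% CI, and set beside it the numbers pre-screened, approved by the oncologist and consented. Make no claim for all patients recommended or receiving pelvic RT. If Appendix 2 does provide for ratings from a wider group, say so in the body and define the denominator to match.

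The cost is wording only, with no new data collection. The downside is a narrower stated scope.

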13. SAFETY MANAGEMENT

13.1 Regulatory and Ethical Considerations

13.1.1 Data and Safety Monitoring Plan

The Inova PI will monitor and review the study progress, participant safety, and the accuracy and security of the data.

13.1.1.1 Communication Plan

The DSM plan is adequate as the study will be limited to only Inova sites.

13.1.2 Risk Assessment

There is very low risk to this research intervention. The integration of exercise therapy is recommended by NCCN and ASCO for cancer patients and survivors to reduce the relapse risk and mitigate the side effects of therapy, including fatigue (2, 13). It is possible that exercise could worsen fatigue or side effects of treatment, although this likelihood is felt to be low. Patients may feel sore from activity if they were not previously active, but this would be temporary and not cause a risk of harm to the patient. As such, this study would not be greater than minimal risk of harm.

13.1.3 Potential Benefits of Trial Participation

The integrated check-ins for each arm of the trial exercise program may provide benefit in improving patient-reported outcomes and support cancer patients in a structured format. The indirect benefits of this study may be that it sets up our group to continue an exercise oncology research

program that can provide additional literature to healthcare payors for the reimbursement of exercise therapy programs for patients undergoing radiation treatments.

13.1.4 Risk-Benefit Assessment

Given that this study would be not greater than minimal risk of harm and the possibility of benefit to the patient herself and future women undergoing pelvic radiation, it is appropriate to proceed with this study.

13.2 Clinical Adverse Events

Clinical adverse events (AEs) will be monitored throughout the study.

13.2.1 Adverse Events Reporting

AEs (including serious AEs) that are felt to be study-related or possibly study-related will be noted in the study records and on the case report form with a full description including the nature, date, and time of onset, determination of non-serious versus serious, intensity, (mild, moderate, severe), duration, causality, and outcome of the event.

SAEs are not expected because the study procedures are not greater than minimal risk. If any unanticipated problems related to the research involving risks to participants or others happen during this study (including SAEs), they will be reported to the IRB in accordance with Policy – Reporting of Adverse Events, Unanticipated Problems and Protocol Violations, ORI 11.16. AEs that do not meet prompt reporting requirements will be summarized in the narrative or other format and tracked and documented internally by the study team but not submitted to the IRB.

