Number of Participants:	
16 participants randomized 1:1 to immediate start or delayed start intervention
 
Stratification will be performed to divide the number of patients with no to mild fatigue (0-3 numeric rating scale) from patients with moderate to severe fatigue (4-10) because it is possible that the intervention effect is variable depending on baseline level of fatigue.

Study Duration:	Each participant's participation will last up to 6 months.
Study Phases:	Screening for eligibility and obtaining consent
Screening	
Study Treatment	
The exercise coaching program will consist of weekly check-ins for 10 weeks with a certified exercise coach with expertise in caring for oncology patients with a goal of increasing activity to 150 minutes of moderate activity per week. This will be accomplished by shaping behavior through personalized recommendations. Women randomized to the immediate start group will start the intervention during the first week of radiation therapy and continue through and post-completion of radiation. Women randomized to the delayed start group will start the intervention at 6-8 weeks post-radiation.

Follow-Up	Steps, active minutes, patient-reported fatigue, bowel/urinary toxicity, QoL, cognitive function, sexual function and satisfaction, and self-efficacy, as well as distance walked during 6MWT.

Efficacy Evaluations:	
Steps, active minutes, and heart rate measured by a Fitbit device
 
PROMIS Short Form v1.0 – Fatigue 13a (FACT-Fatigue)
 
EPIC Prostate Bowel and Bladder assessment (short form)
 
PROMIS-29 Profile v2.1 QoL (physical function, anxiety, depression, sleep disturbance, pain interference/intensity, ability to participate in social roles and activities)
 
PROMIS Short Form v2.0 – Cognitive Function 4a
 
PROMIS Sexual Function and Satisfaction v2.0 Brief Profile (Female)
 
PROMIS Short Form v1.0 – Self-Efficacy for Chronic Conditions – Managing Daily Activities 4a and Managing Symptoms 4a
 
6MWT

Safety Evaluations:	
Patients can communicate any concerns or safety issues during their weekly check-ins with the exercise coach. They will also be provided with information for contacting an on-call doctor as part of usual care to report any concerning symptoms should they occur outside of the standard evaluation schedule.

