6. STUDY TIMELINE

6.1 Individual Participation

The study duration per participant will be up to six months. Patients will be requested to wear their Fitbit from the start of enrollment to the 16-19 weeks post RT visit, participating in standard-of-care weekly visits during RT at 5-7 weeks post RT, and again 16-19 weeks post RT. The ten consecutive weekly exercise coaching check-in sessions will start for the early intervention during the first week of RT and the delayed intervention at 6-8 weeks post RT.

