9.3.8 Bi-weekly active attention control check-ins x 10 weeks

- Early intervention cohort: Check-ins, once every 2 weeks, with an approximately 5-minute telephone call by a research coordinator to start the week following completion of their exercise intervention (approximately 5 weeks after pelvic RT) for a total of 5 calls.
- Delayed intervention cohort: Check-ins, once every 2 weeks, with an approximately 5-minute telephone call by a research coordinator starting during the first week of RT (Fx 1-5) and continue for 10 weeks for a total of 5 calls.
- The research coordinator will inquire about their use of the Fitbit device, such as if they are wearing it regularly, any technical issues, and if they are syncing their data without discussing physical activity.

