17.1 Discontinuation of Study Intervention

Discontinuation from study intervention does not mean discontinuation from the study, and the remaining study procedures should be completed as indicated by the study protocol. If a clinically significant finding is identified (including, but not limited to, changes from baseline) after enrollment, the investigator or qualified designee will determine if any change in participant management is needed. Any new clinically relevant finding related to study participation will be reported as an adverse event (AE).

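### Adverse events reach the case report form only if felt to be study-related, and safety contact follows coaching, so injury counts during radiation are not comparable between arms

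*Protocol*

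**What the plan says.** Section 13.2 of the protocol promises that "Clinical adverse events (AEs) will be monitored throughout the study" but gives no method or schedule. Section 13.2.1 then sets the recording rule: "AEs (including serious AEs) that are felt to be study-related or possibly study-related will be noted in the study records". The same rule governs entry on the case report form, where the description must include causality. Its last sentence says that events not needing prompt reporting are summarised and tracked internally, and does not mention relatedness. Section 17.1 also ties reporting a new finding as an AE to its relation to study participation.

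The synopsis row on safety evaluations gives two routes for concerns. The first is study-specific: "Patients can communicate any concerns or safety issues during their weekly check-ins with the exercise coach". The second is open to everyone: "They will also be provided with information for contacting an on-call doctor as part of usual care to report any concerning symptoms". Section 6.1 adds clinic contact in both arms: "participating in standard-of-care weekly visits during RT at 5-7 weeks post RT, and again 16-19 weeks post RT". The coordinator calls in section 9.3.8 ask about wear, technical problems and "if they are syncing their data without discussing physical activity".

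Section 13.1.2 names the harm in view: "It is possible that exercise could worsen fatigue or side effects of treatment". Sections 5.3 and 10.2 state that allocation is open to patient and physician.

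**The concern.** A rule that records an event only after someone has judged it related puts the causality decision before data capture. In an open trial that decision can depend on the arm. A fall or strain in a woman being coached can readily be called possibly related. The same event in a delayed-arm woman during RT, before any coaching, usually cannot. The study contact at which safety concerns are invited also exists only while a woman is coached. Both mechanisms push recorded events towards the coached arm and period.

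At stake is what the pilot can hand on about events the questionnaires do not record. The intervention is unmonitored exercise, and section 7.1 screens for fall risk and for cardiac and pulmonary conditions, so these are the events a follow-up trial would want to describe. A primary aim is to find data-management problems before a full-scale trial, and arm-dependent capture is one of them.

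**Working it through.** The protocol states no AE rate, power or safety figure to reproduce. The check compares the text and then adds simple arithmetic.

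**1. Delayed-arm time without a coach.** Table 1 shows 25 fractions in five weekly blocks, so RT lasts 5 weeks. Section 9.3.7 starts delayed coaching 6 to 8 weeks after RT. From RT start: 5 + 6 = 11 to 5 + 8 = 13 weeks.

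**2. Study contact in the first 10 weeks from RT start.**
- Early arm (9.3.7): one session of 60 minutes and nine of 30, so 60 + 9 × 30 = 330 minutes with a coach.
- Delayed arm (9.3.8): five calls of about 5 minutes, so 5 × 5 = 25 minutes. Table 1 allows 5 to 10 minutes per call, so at most 5 × 10 = 50. No safety question is listed.

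These minutes measure opportunity to report, not events captured, and they leave out the weekly RT visits that both arms share.

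**3. Two readings of section 13.2.1.**
- If the first sentence governs, an event felt to be unrelated is not entered, and causality becomes a field on a form that only events already judged related can reach.
- If the last sentence covers all events, it conflicts with the first on what is documented. Unrelated events are then logged internally, but still without a common question in both arms.

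Capture depends on arm under the first reading through filter and contact, and under the second through contact.

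**4. What unequal capture can do (assumed inputs).** Observed rate = true rate × proportion captured. Assume a true rate of 30% in both arms and 90% capture in the coached arm: 0.30 × 0.90 = 0.27.

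| Capture, uncoached arm | Observed rate | Apparent risk ratio |
|---|---|---|
| 90% | 0.27 | 0.27 / 0.27 = 1.0 |
| 60% | 0.18 | 0.27 / 0.18 = 1.5 |
| 30% | 0.09 | 0.27 / 0.09 = 3.0 |

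The protocol gives none of these proportions. The table shows direction and range only.

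**5. What remains after perfect capture, 8 per arm.**
- Exact two-sided 95% upper limit for 0 of 8: 1 − 0.025^(1/8) = 0.369, or 37%.
- Fisher's exact test: 4 v 0 gives p = 0.077; 5 v 0 gives p = 0.026.

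**6. Outcomes the rule does not touch.** FACIT-F, EPIC and the 6MWT are scheduled for all participants at enrolment, RT week 5, 5–7 weeks and 16–19 weeks post RT (9.3.1, 9.3.4 to 9.3.6), and section 12.2 compares them by intention to treat. With 8 per arm the 95% interval half-width is t(0.975, 14) × √(2/8) = 2.145 × 0.5 = 1.07 SD. The difference detectable with 80% power at two-sided 0.05 (assumed levels) is about 1.51 SD by the noncentral t.

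**The case against.** The strongest reply is that the harm named in section 13.1.2 is measured without any relatedness filter, in both arms, on the same schedule. That stands. A reader might infer from the AE rule that the pilot cannot show whether exercise during RT worsens fatigue or toxicity. The documents do not support this: FACIT-F and EPIC carry that comparison, and its weakness is 8 per arm.

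A reader might also infer that the coach is the only route for reporting a problem. The synopsis and section 6.1 contradict that, since the on-call doctor and weekly RT visits exist in both arms. What survives is that neither is described as a step at which AEs are collected for the study.

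Nor is the delayed arm's count forced to zero. The threshold includes possible relation, and these women wear the Fitbit and walk the 6MWT in RT week 5, so an injury during that test could be recorded. PROMIS-29 also captures pain and physical function in both arms, though as scores rather than events.

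Chart variables, coach notes and the exit interview are defined in appendices that are not shown, and these may bring in further events. Comparative safety is not an objective, and 16 patients cannot supply it. These points limit the size of the concern. They do not remove the stated filter or the unequal contact.

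**Conclusion.** The point holds in limited form. Followed as written, section 13.2.1 and the contact schedule make counts of falls, musculoskeletal injury and cardiopulmonary events non-comparable between arms during RT, and the wording leaves the handling of unrelated events unclear. The size of the distortion cannot be computed from the protocol. Under the assumed capture rates above, the apparent risk ratio runs from 1.0 to 3.0 with no true difference.

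The conclusion assumes that the unseen appendices do not already require collection of these events in both arms regardless of attribution. It does not extend to fatigue or bowel/urinary toxicity. This is a worthwhile, inexpensive improvement to a feasibility pilot, not a threat to its primary objective.

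**What to change.** In section 13.2.1, and consistently in 17.1, record serious AEs, falls, musculoskeletal injury and cardiopulmonary events in both arms from enrolment to the 16–19 week visit regardless of attribution, and assign causality afterwards. Reconcile the first and last sentences of 13.2.1 so that the handling of unrelated events is explicit.

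Ask the same short, neutral question, without reference to physical activity, at the coordinator calls, coach check-ins and assessment visits already scheduled. Report the events descriptively by arm and by period (RT to 5–7 weeks; 5–7 to 16–19 weeks post RT).

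The cost is protocol wording, one case report form page and a minute or two per call for 16 patients. The downside is that a few more events attributable to RT will be logged, and the counts will still support description only.
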